4. STATISTICAL CONSIDERATIONS

4.1 Sample Size and Power

The primary analysis will be based on HIV incidence during Steps 1 and 2. As described previously, we assume that participants will be followed between 81 (latest enrollees) and 185 (earliest enrollees) weeks in Steps 1 and 2 (1.6 – 3.6 years), with a uniform distribution of enrollments over a two-year period. Thus, average time in Steps 1 and 2 will be 133 weeks (2.6 years). Sample size calculations are based on the following assumptions:

- Background HIV incidence, in the absence of any PrEP, is 3.5% per year
- Both CAB LA and TDF/FTC are 85% effective when used with 100% adherence
- 2.5% one-sided type I error rate and 90% power at the indicated alternative
- Average follow-up duration of 2.6 years (range: 1.6 – 3.6 years)
- Maximum 5% lost-to-follow-up per year

Table 4.1 presents five scenarios and associated total sample sizes. All are superiority designs. The first scenario assumes that adherence to TDF/FTC and CAB/CAB LA will be 50% and 85%, respectively, averaged over the entire Step 1 and 2 follow-up period. The second and third scenarios assume a higher adherence to TDF/FTC (second line) and lower adherence to CAB LA (80%) (third line) (these scenarios are considered unlikely). The last two scenarios retain the conservative assumption of 80% adherence to CAB LA and assume lower adherence to TDF/FTC of 45% and 48%. The largest blinded trials of TDF/FTC among women in a similar setting have shown even lower adherence than assumed in Table 4.1.

Given this history we believe that a sample size of at least 3,128 (111 events for a fixed sample size trial; we will target 114 events to allow for interim monitoring) provides an adequate degree of robustness against uncertainties in adherence rates to the two drug regimens. The trial will continue until we reach 114 events, or a stopping boundary is crossed (see below).

Table 4.1. Five Case Scenarios

Adherence		HIV Incidence (%/year) ¹				
TDF/FTC	CAB LA	TDF/FTC	CAB LA	RR	Number Events	Sample Size
.50	.85	2.01	0.97	.48	78	2352
.55	.85	1.86	0.97	.52	98	3112
.50	.80	2.01	1.12	.56	125	3590
.48	.80	2.07	1.12	.54	111	3128
.45	.80	2.16	1.12	.52	98	2686

¹Background incidence is reduced by a weighted average of fully adherent and non-adherent individuals e.g. 2.01 = $3.5 * ((1 - .85) * .5 + 1 * (1 - .5))$

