Adherence in the TDF/FTC arm will be measured during the trial in an adherence assessment cohort (see below). If adherence in the TDF/FTC arm is greater than 50% then an NI margin will be computed as described in section 7.8.4.3 of the protocol. The primary analysis described above will then be repeated using the recomputed NI margin instead of 1.0 in the null hypothesis. This supportive NI analysis will not replace the pre-specified primary analysis or change the conclusion of the primary analysis but may provide valuable insight with respect to determining the prevention effectiveness of CAB LA in women.

7.3.1.2. Adherence Assessment Cohort:

A sample of 400 participants in the active TDF/FTC arm will be selected at random during the enrollment period and available plasma samples from selected visits (Step 1: week 4; Step 2: weeks 9, 17, 33, 57, 81, 105, 129, 153, 177) will be assessed for the presence of TDF/FTC and associated metabolites. The TDF/FTC adherence-assessment cohort will be stratified by site or

region and will be selected to ensure uniform representation over the course of the enrollment period. Average, study-wide adherence will be computed as the overall proportion of all tested samples where study drug (TDF/FTC) is detected (i.e. concentrations greater than approximately 0.31 ng/ml).

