7.3.4. Adverse events Step 2 only OBSP

Objective: To compare the safety of CAB LA vs. oral TDF/FTC proximal to blinded study drug administration

Population: Step 2 safety

Censoring: AEs are censored using ON BLINDED STUDY PRODUCT (OBSP) censoring.

Details of the OBSP censoring definitions are given in Appendix B. Reported AEs will be excluded if they occur before the first injection or after the OBSP censoring time.

Descriptive and Statistical Analysis will be performed as above

7.3.5. *Laboratory evaluations*

Population: Primary Safety

Descriptive: Laboratory findings for CBC, chemistries (urea, creatinine, CPK, glucose, calcium, phosphorous, amylase, lipase), liver function (AST, ALT, total bilirubin, alkaline phosphatase) and fasting lipid profile (total cholesterol, triglycerides, HDL, LDL) will be reported by grade, as defined in the “Division of AIDS (DAIDS) Table for Grading the Severity of Adult and Pediatric Adverse Events”. The proportion of laboratory findings qualifying as Grade 2 or above will be presented. Laboratory values will be reported by arm as median, 1st and 3rd quartiles, min and max, and (at follow-up visits) as median, 1st and 3rd quartile change from baseline (see below). Summaries involving values and changes from baseline at scheduled visit time points will consider values from scheduled visits only, and in the case of missing values, results will not be carried forward from interim (unscheduled) visits. For summaries and analyses involving changes in laboratory values over time or maximum change from baseline (e.g. shift tables), values from interim (unscheduled) visits will also be considered.

Formal comparisons of laboratory values will be conducted as follows:

- Absolute values: A mixed-effects model with participant as the random effect and site and arm as fixed effects will be used to assess overall differences in each laboratory outcome by arm. Outcomes with highly skewed distributions will be log-transformed. A continuous time (elapsed study time) term and an interaction of time with study arm will be added to model time trends in laboratory values that may emerge with continuous exposure to study drug. Only post baseline visits will be included.

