The proportion of participants reporting any high-risk behavior will be assessed at each visit. Mixed effects logistic regression will be used to estimate prevalence and 95% confidence intervals for each behavior. Time trends during follow-up will be estimated using mixed effects logistic regression. Linear and non-linear models (with respect to time) will be explored.

Rates of incident STI's will be computed as number of new STI's divided by total person-years. Poisson regression with a robust variance will be used to model the number of incidents STI for each woman. Person-time will be used as an offset. Incidence and a 95% CI will be reported overall and by arm.

b. **Objective:** To compare Grade >2 adverse event (AE) rates in women with baseline BMI $</\geq 25$ kg/m², within each study arm.

Population: Primary Safety Population

Outcome: Counts of grade 2 or higher AE

For each arm, tables will summarize the number of grade 2 or higher AEs by MedDRA System Organ Class and BMI. Participant with multiple AEs within a category will be counted once under the maximum severity. The overall grade 2 or higher event rate and a 95% confidence interval will be calculated for those with BMI $<$ and ≥ 30 kg/m² at baseline based on a log-linear model for counts using log(person-time) as an offset, assuming a Poisson distribution, and using a robust variance (i.e. generalized estimating equations). Event rates will be compared between those with BMI $<$ and ≥ 30 kg/m² at baseline using a similar model.

c. **Objective:** To compare differences in weight gain, by arm.

Population: Primary Safety Population

Outcome: Weight (kg)

Weight gain will be computed as change from baseline (enrollment) at each follow-up visit. We will plot mean weight gain over follow-up by treatment arm. A linear mixed model with random person and time effects will be fit with (i) continuous time and (ii) categorical intervals for time in study, treatment and time by treatment interaction to evaluate the effect of CAB LA on weight gain. The interaction between time and treatment will quantify the difference in weight gain by arm. A second analysis that removes women when they become pregnant will be conducted.

d. **Objective:** To compare pregnancy incidence and outcomes between arms.

Population: mITT Population and PREGNANCY Subgroup Population

Outcome: New pregnancies and pregnancy outcomes

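### The absolute-value laboratory model in SAP 7.3.5 tests a time-by-arm slope with only a participant random effect, so that test can be anti-conservative when women's trends differ; a minor point with a one-phrase fix

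*SAP*

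**What the plan says.** SAP 7.3.5, Absolute values, specifies: "A mixed-effects model with participant as the random effect and site and arm as fixed effects will be used". It continues: "A continuous time (elapsed study time) term and an interaction of time with study arm will be added to model time trends", the target being "time trends in laboratory values that may emerge with continuous exposure to study drug". On the data it says "Only post baseline visits will be included". No random time effect, serial correlation structure or robust variance is named for this model.

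Two other parts of the SAP handle within-woman dependence more fully. For weight, 7.3.7c states "A linear mixed model with random person and time effects will be fit with (i) continuous time" and reads the time-by-treatment interaction as the difference in weight gain. For adverse event rates, 7.3.2 specifies a robust variance.

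The note that closes 7.3.5 says the formal laboratory comparisons will not appear in the Clinical Study Report, and 9.2 repeats this.

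**The concern.** The usual reading of a model with participant as its one random effect is y = site + arm + time + arm × time + participant intercept + error. The only within-woman correlation this allows is a constant shift per woman. The emerging-trend question is answered by arm × time, a difference in slopes, from which a constant shift drops out. If women have their own trends, the model treats those departures as independent visit noise and credits the interaction with more precision than it has.

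The SAP gives some reason to expect unequal trends. Table 4.1 assumes 45–55% adherence to TDF/FTC, and its footnote describes a mixture of fully adherent and non-adherent women. A trend driven by exposure would then differ between women within an arm.

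At stake are intervals for the interaction that are too narrow, and hence possible spurious signals of emerging laboratory change for either product. Section 7.3.5 lists 16 named analytes plus CBC, and several bear on adverse events of special interest in Appendix E (hepatic, creatinine, glucose, pancreatic).

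**Working it through.** The SAP states no standard error, alpha or slope SD for this model, so there is no figure of its own to reproduce.

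**Inputs from the SAP**
- Follow-up (4.1): "we assume that participants will be followed between 81 (latest enrollees) and 185 (earliest enrollees) weeks in Steps 1 and 2".
- Allocation 1:1 (4.2).

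**Assumptions**
- Visit times: the SAP gives no laboratory sampling schedule, so the adherence-cohort plasma weeks in 7.3.1.2 stand in: "Step 1: week 4; Step 2: weeks 9, 17, 33, 57, 81, 105, 129, 153, 177".
- Between-woman slope SD (sb): 0.1 to 0.5 residual SDs per year.
- Residual SD s = 1.
- A nominal two-sided 5% Wald test.

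**Closed form, m common visits per woman.** Let Sxx be the sum of squared deviations of the visit times, in years.
- True variance of one woman's fitted slope: sb² + s²/Sxx.
- Variance that the random-intercept model reports: s²/Sxx + sb²/(m−1).
- Variance ratio R = true/reported. False-positive rate = 2 × [1 − Φ(1.96/√R)].

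The two variances agree when sb = 0 or m = 2. For m ≥ 3 and sb > 0 the reported variance is the smaller. With r = sb²·Sxx/s², R = (1+r)/(1+r/(m−1)). For example, m = 8 and r = 1 give R = 2/(1+1/7) = 1.75 and a false-positive rate of 13.8%.

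**Worked case: 10 visits to week 177, sb = 0.3.** Sxx = 35,166.5/52² = 13.005.
- True variance: 0.09 + 0.0769 = 0.1669.
- Reported variance: 0.0769 + 0.09/9 = 0.0869.
- R = 1.92, so the reported standard error is 0.72 of the true one and the false-positive rate is 15.7%.

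**False-positive rate of the time-by-arm test (closed form)**

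| Visits | sb 0.1 | 0.2 | 0.3 | 0.5 |
|---|---|---|---|---|
| 2 (weeks 17, 105) | 5.0% | 5.0% | 5.0% | 5.0% |
| 3 (weeks 17, 57, 105) | 5.1% | 5.3% | 5.7% | 6.8% |
| 6 (to week 81) | 5.2% | 5.6% | 6.4% | 8.7% |
| 8 (to week 129) | 5.6% | 7.2% | 9.8% | 16.7% |
| 10 (to week 177) | 6.3% | 10.2% | 15.7% | 26.7% |

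**Simulation with staggered follow-up.** There was no arm difference, 400 women, follow-up uniform on 81–185 weeks, the same visit weeks, intercept SD = residual SD = 1, REML, and 400 runs per setting. The Monte Carlo standard error at 5% is √(0.05 × 0.95/400) ≈ 1.1 points.

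| Slope SD | Random intercept only | Reported SE / actual SD | With random slope added |
|---|---|---|---|
| 0 | 5.0% | 1.00 | 4.5% |
| 0.1 | 5.2% | 0.96 | 4.5% |
| 0.2 | 6.8% | 0.91 | 4.3% |
| 0.3 | 11.7% | 0.82 | 4.3% |
| 0.5 | 20.3% | 0.66 | 4.8% |

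The simulation agrees with the closed form in direction and order of size. Adding the random slope returns the test to its nominal level within simulation error.

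**The case against.** The case for leaving the text alone has four parts.

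1. **Role.** A reader might infer that this interaction is how the trial detects emerging laboratory toxicity. The SAP does not give it that role. Laboratory safety rests mainly on grade tables, change from baseline and shift tables (7.3.5, 9.2), on box plots and Grade 3 or higher tabulations for the DSMB (9.1), and on the special-interest event review (Appendix E). The primary safety comparison is adverse events of grade 2 or higher (7.3.2). The laboratory models carry no stated alpha or decision rule, and their results stay out of the Clinical Study Report. This stands, and it caps the severity.

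2. **Size.** The inflation may be negligible: 5.2% in the staggered simulation at slope SD 0.1. The large figures need strong drift. With intercept and residual SDs of 1, a slope SD of 0.5 adds 0.25 × (185/52)² = 3.16 to a variance of 2 by week 185, an increase of about 158%. Nothing in the SAP shows that any listed analyte behaves this way. This stands too, so the figures can only be given as a conditional range.

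3. **Generality.** A reader might infer that the standard error is too small whenever trends differ. With two values per woman it is not. The claim needs three or more, which 81–185 weeks of follow-up makes likely but which the SAP does not state.

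4. **Weight model.** A reader might see 7.3.7c as contradicting 7.3.5. It does not: weight gain is a listed tertiary objective and modelled laboratory trends are not, so the two may be specified differently. The weight model shows only that the better specification is already in use.

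None of this answers the core point. As written, the model has no term for slope variation in a test about slopes.

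**Conclusion.** The point holds as a minor one. Reading participant as the sole random effect to mean a random intercept, and with three or more post-baseline values per woman, any variation in individual slopes makes the model-based standard error of the time-by-arm interaction too small. Over slope SDs of 0.1–0.5 residual SDs per year, the false-positive rate of a nominal 5% test runs from about 5–9% (6 visits to week 81) to 6–27% (10 visits to week 177). Those figures rest on an assumed slope SD and a borrowed visit schedule.

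The documents do not support extending this to the overall arm comparison of laboratory values, the model's first stated use, which was not shown to be affected. The primary efficacy and primary safety analyses are untouched. The separate change-from-baseline model in 7.3.5 is outside this point.

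**What to change.** In SAP 7.3.5, Absolute values, replace the phrase naming participant as the random effect with: *random participant intercept and random participant slope for elapsed study time*, matching the weight model in 7.3.7c. Add that participant-clustered robust standard errors will be used if this model does not converge for a given analyte.

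The cost is one phrase and one model option, with slightly wider intervals for the interaction and an occasional fallback. Because these comparisons are not part of the Clinical Study Report, its programming is not affected.

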- Change from baseline. A fixed effect model with site and arm as covariates will be used to assess overall change from baseline for each laboratory outcome by arm. A continuous time (elapsed study time) term and an interaction of time with study arm will be added to model differences in laboratory values that may emerge with continuous exposure to study drug.

Note: Formal comparisons of laboratory values as described above will not be included in the Clinical Study Report.

7.3.6. *Secondary Analyses*

- a. **Objective:** To compare HIV incidence among participants receiving oral CAB/CAB LA vs. daily oral TDF/FTC (Steps 1, 2 and 3).

Population: mITT population

Outcome: Time of HIV-1 Infection

This analysis will be similar to the primary analysis of HIV incidence but will include the entire follow-up period (steps 1, 2 and 3) for each participant. The analysis will be based on a Cox model using time to HIV detection (as defined in the primary analysis) as the outcome. The model will include an indicator for intervention arm (TDF/FTC = 0; CAB LA = 1) and be stratified by site. Participants who remain HIV-1 uninfected will be censored at their last negative HIV test. A formal statistical comparison between study arms will be performed using a Wald test of the hypothesis

Ho: HR = 1

Ha: HR < 1

A one-sided test with $\alpha = .025$ will be used. The estimated hazard ratio (HR), a 95% confidence interval, and a p-value for the hypothesis shown above will be given.

b. **Objective:** To evaluate relative efficacy of oral CAB/CAB LA vs. oral TDF/FTC in subgroups defined by the baseline factors of age, herpes simplex virus-2 (HSV-2) serostatus, and body mass index (BMI).

Population: mITT population

Outcome: Time of HIV-1 Infection

These analyses will be similar to the primary analysis of HIV incidence and will include data from follow-up steps 1 and 2 for each participant. The number of events, person-years and incidence will be calculated for each arm within each subgroup.

Subgroups will be defined as follows:

Age (<25 vs ≥ 25)

HSV-2(positive or negative)

BMI (<30.0 vs ≥ 30.0)

Contraceptive method during treatment (DMPA, Net_EN, Implants, Other)

Age, HSV-2 and BMI will be based on baseline status while contraception will be treated as a time-varying covariate.

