Laboratory results will be summarized by scheduled study visit. Summary calculations such as maximum post-baseline level will include data from interim (unscheduled visits). Formal comparisons of laboratory findings between arms will not be included in the CSR.

- **Adverse Events**

The reporting of safety data is descriptive and will include all subjects who receive at least one dose of investigational product. AEs will be summarized based on the frequency of AEs and their severity for all treated subjects. All AEs will be coded using Medical Dictionary for Regulatory Activities (MedDRA) and summarized by treatment group. Data will be summarized using preferred term and primary system organ class.

If a subject experiences multiple events that map to a single preferred term, the greatest severity will be assigned to the preferred term for the appropriate summaries.

Summaries of AEs will include any AEs reported beginning with the first dose of investigational product on Day 1. The occurrence of adverse events will be summarized by treatment group using preferred terms, system organ classifications, and severity. Separate summaries of serious adverse events, adverse events related to investigational product, and events leading to the discontinuation of investigational product will be generated. All adverse events reported will be listed for individual subjects showing both verbatim and preferred terms.

- **Efficacy and Efficacy Subgroups**

In the Clinical Study Report, primary efficacy analysis will be presented as described in Section 7.3.1. For subgroup analyses, the age and BMI subgroup analyses will be presented in the Clinical Study Report, but analyses considering contraceptive use and HSV-2 status at baseline will not be presented in the Clinical Study Report.

10. Summary of changes

10.1 Version 3.0 was prepared during the planning process for the Clinical Study Report. The blinded statistician continued to not have access to individual level data.

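### The laboratory change-from-baseline model makes no allowance for repeated measurements on the same woman, so the standard error of its overall arm difference is too small

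*SAP*

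**What the plan says.** Section 7.3.5 (Laboratory evaluations) sets out two formal between-arm models, one directly after the other.

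- **Absolute values:** "A mixed-effects model with participant as the random effect and site and arm as fixed effects will be used", with elapsed time and time-by-arm added, on post-baseline visits.
- **Changes, second bullet:** "A fixed effect model with site and arm as covariates will be used to assess overall change from baseline for each laboratory outcome by arm". Then: "A continuous time (elapsed study time) term and an interaction of time with study arm will be added to model differences in laboratory values". The bullet names no participant effect, residual covariance, GEE or robust variance, and it does not say which visits enter.

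Three other statements bear on the point.

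- Section 7.1.1 takes the Day 0/randomization value as baseline, so all of a woman's changes share it.
- Section 7.3.5 gives a rule for "For summaries and analyses involving changes in laboratory values over time or maximum change from baseline (e.g. shift tables), values from interim (unscheduled) visits": these are considered as well as the scheduled ones.
- The formal models have a limited role: "Formal comparisons of laboratory values as described above will not be included in the Clinical Study Report". Section 9.2 repeats this: "Formal comparisons of laboratory findings between arms will not be included in the CSR".

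Elsewhere the SAP does deal with correlation within a woman. The weight-change analysis in 7.3.7c reads "A linear mixed model with random person and time effects will be fit with" continuous and categorical time. The drug-concentration regression (7.3.6d) uses GEE with robust variances. The event-count and pregnancy models (7.3.2, 7.3.7b, 7.3.7d) use a robust variance, and the contraceptive-level t-test (7.3.7f) does so when a woman has several observations.

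**The concern.** Arm is constant within a woman. If she contributes several correlated changes and the model treats them as independent, the information about the arm difference is overstated and its standard error understated. The overall arm comparison would then be significant by chance more often than its nominal level.

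Section 7.3.5 lists 16 analytes besides the CBC, including AST, ALT, creatinine, CPK and lipase. Several relate to the adverse events of special interest in Appendix E (hepatic safety, creatinine, rhabdomyolysis, pancreatitis). Spurious arm differences in these would be awkward to interpret, and could conflict with the mixed model for the same outcomes partly because one standard error is wrong.

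**Working it through.** The SAP gives no standard error, power, laboratory schedule, correlation or alpha for this model, so there is no stated figure to reproduce. What follows is an illustration. The assumptions are a two-sided 5% level, *m* records per woman, and correlation *rho* between her changes.

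**1. Do several changes per woman enter?** The bullet parallels the repeated-visit model before it, adds the same elapsed-time terms to capture differences emerging with continuous exposure, and names no single last or maximum value. The unscheduled-visit rule adds further eligible values. Repeated changes are the natural reading.

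**2. Can *fixed effect* mean one effect per participant?** No. Arm does not vary within a woman, so it could not then be estimated.

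**3. Does subtracting baseline remove the correlation?** It removes the woman's level but puts the same baseline error into each change. With within-woman variance s² and otherwise independent visits:

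- variance of a change = s² + s² = 2s²
- covariance of two changes = s²
- correlation = s²/(2s²) = 0.5, whatever the intraclass correlation of the absolute values

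**4. Effect on the overall arm difference (no interaction term).**

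- Design effect DE = 1 + rho(m − 1)
- Ordinary SE / true SE = 1/√DE
- Actual type I error = 2[1 − Φ(1.96/√DE)]

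Example, rho = 0.5 and m = 5: DE = 1 + 0.5 × 4 = 3; SE ratio = 1/√3 = 0.58; type I error = 2[1 − Φ(1.96/1.732)] = 0.258.

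| Records per woman | SE ratio, rho 0.5 | Type I, rho 0.3 | Type I, rho 0.5 | Type I, rho 0.7 |
|---|---|---|---|---|
| 1 | 1.00 | 0.050 | 0.050 | 0.050 |
| 2 | 0.82 | 0.086 | 0.110 | 0.133 |
| 5 | 0.58 | 0.186 | 0.258 | 0.315 |
| 10 | 0.43 | 0.308 | 0.403 | 0.468 |
| 15 | 0.35 | 0.390 | 0.488 | 0.551 |

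At rho = 0.5 with 5 records and no true differences, about 16 × 0.258 = 4.1 of the 16 analytes would be nominally significant, against 16 × 0.05 = 0.8 expected.

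**5. Simulation with no true arm effect.** Two set-ups were run.

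- *400 women, 20 sites, site and arm in the model, 1,500 runs, no slope variation.* Ordinary regression rejected 0.169–0.173 (3 records), 0.262–0.265 (5) and 0.405–0.428 (10). The arm effect at mean time, after adding time and arm-by-time, gave practically the same rates. Clustering the variance by woman gave 0.041–0.065 for the overall arm difference, including two further runs with slope variation.
- *1,000 women, 1:1, time scaled to (0,1], 2,000 runs.* Slope SD is in units of the within-woman SD.

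| Test, ordinary SE | Slope SD | 5 records | 10 records | 15 records |
|---|---|---|---|---|
| Overall arm | 0 | 0.268 | 0.378 | 0.477 |
| Overall arm | 3 | 0.292 | 0.460 | 0.544 |
| Arm at time 0, interaction in model | 0 | 0.052 | 0.105 | 0.174 |
| Arm at time 0, interaction in model | 3 | 0.000 | 0.009 | 0.033 |
| Arm-by-time | 0 | 0.008 | 0.006 | 0.006 |
| Arm-by-time | 3 | 0.030 | 0.116 | 0.201 |

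In this second set-up cluster-robust standard errors gave 0.046–0.057 for the overall arm difference and 0.044–0.060 for the interaction.

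The inflation is consistent for the overall arm difference. For the interaction, and for the arm coefficient at time 0, the ordinary test may be too liberal or too conservative, depending on how much slopes vary between women.

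**The case against.** The strongest reply is that both premises are inferred. Planned follow-up runs from 81 to 185 weeks (section 4.1), so elapsed time would differ between women even with one change each, and the time terms could still be estimated. The unscheduled-visit rule also covers maximum change, which is one value per woman. The move from a mixed to a fixed effect model could therefore be deliberate. *Fixed effect* might also describe only the mean structure and leave the covariance to be filled in.

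This is right to the extent that the time terms do not prove repeated records, and with one change per woman there is no error. But that reading is strained: the bullet names no last or maximum value, and it mirrors the repeated-visit model beside it. As for an unstated covariance, the adjacent bullet names its participant effect, the SAP's other repeated-measure analyses cited above name a correction, and section 7.1 has no general rule that supplies one here. Followed as written, the bullet leads to ordinary standard errors.

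Two further points stand. The magnitudes rest on assumptions, and the interaction results have no consistent direction, so the claim must be confined to the overall arm difference. The consequence is also small: the comparisons are outside the Clinical Study Report and are not the primary safety analysis. Some disagreement between change and absolute-value models can arise even with correct standard errors.

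**Conclusion.** The concern holds, as a minor one. With repeated changes per woman, the model as written understates the standard error of the overall arm difference. Under a two-sided 5% level and correlation 0.5, the actual error is 11–21% for 2–4 records, 26–49% for 5–15 and 51–62% for 17–30. For 5–15 records the range is 19–39% at correlation 0.3 and 32–55% at 0.7. The direction follows from the model and any positive correlation. The size depends on a visit count and a correlation that the SAP does not give.

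No primary result is affected. Exclusion from the Clinical Study Report limits the impact, but these remain prespecified comparisons.

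**What to change.** In the change-from-baseline bullet of section 7.3.5, add the participant random effect already used for absolute values, with a random time effect as in the weight model of 7.3.7c; or keep the mean model and use cluster-robust (GEE) standard errors by participant. The random participant effect matches the shared-baseline structure exactly when slopes do not vary; the cluster-robust option was the one checked by simulation, with and without slope variation.

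State which visits enter, including whether unscheduled ones do. If a single change per woman is intended, define it (for example, last or maximum) and the correlation issue falls away. Adjusting for the baseline value could add precision but is not needed for this correction.

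The cost is one sentence of SAP text and a standard software option. No new data are needed.
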